# 5.3.2.2.3. Sensitivity Estimator 3 of the Main Estimand (LOCF)

For this sensitivity estimator 3, the same statistical model, and data included will be used as for the main estimator (Section 5.3.2.1). The assumption for missing data and the rule to handle missing data have changed.

# 5.3.2.2.3.1. Assumptions

- Missing Data for HBsAg are MCAR (Barnes A. et al., 2008)
- The treatment effect is homogeneous across strata

# 5.3.2.2.3.2. Missing Data Handling Rule

For sensitivity estimator 3, participants who withdraw from the study prior to FU Week 24 will be considered as non-responders. After taking into account all the intercurrent events and applying the intercurrent event strategies specified in Section 5.3.2, if a participant who did not experience any ICEs has missing response status for the primary endpoint then the LOCF approach will be used as follows.

If the HBsAg value at FU Week 24 is missing, the LOCF in conjunction with the next available observation imputation approach will be used. The non-missing value closest to FU Week 24 will be selected among the non-missing values which are no earlier than 12 weeks prior to FU Week 24 or no later than 12 weeks after FU Week 24. If 2 non-missing laboratory values are equidistant, the later observation will be preferred. If a participant who did not experience any ICE and does not have HBsAg data within the analysis window of  $\pm 12$  weeks around FU Week 24 assessment will be considered as non-responder.

# 5.3.3. Supplementary Estimand for the Primary Endpoint (Per-Protocol Analysis Set)

The attributes for the supplementary estimand for the primary endpoint are:

#### A) Study Intervention Arms:

- Arm 1: JNJ-3989 + nivolumab (1 infusion) + NA
- Arm 2: JNJ-3989 + nivolumab (3 infusions) + NA
- **B)** Study Population: HBeAg-negative chronic HBV-infected adult patients who are virologically suppressed by being treated with NA.
- **C) Variable:** Individual participant response status defined as whether an individual participant achieved HBsAg seroclearance at FU Week 24 (responders) as defined in Section 5.3.1.

#### **D)** Intercurrent events:

- Treatment discontinuation prior to Week 24: if the participant discontinued treatment prior to Week 24 then s/he will be considered non-responder (composite strategy).
- Deaths prior to FU Week 24 are handled in a composite strategy as participants who die prior to FU Week 24 will be considered as non-responders.

#### E) Population-level summary:

- **a. Primary (comparison vs fixed external proportion):** Difference in proportion of participants with HBsAg seroclearance at FU Week 24 using a fixed external proportion of 1%.
- **b.** Secondary (comparison amongst regimens): Difference in proportion of participants with HBsAg seroclearance at FU Week 24 between study intervention arms.

## 5.3.3.1. Main Estimator of the Supplementary Estimand

#### 5.3.3.1.1. Analysis Methods

Similar methods as described for the main estimator of the main estimand will be used (Section 5.3.2.1.1).

#### 5.3.3.1.2. Data Included

FU Week 24 response status data from randomized participants that are included in the PP analysis set will be used, after taking into account the intercurrent events and applying the intercurrent event strategies specified in Section 5.3.3.

To complement this analysis because of its inherent bias and allow a better interpretation of the results, the proportions of participants excluded from the PP analysis set will be summarized by intervention arm and by type of major protocol deviation.

## 5.3.3.1.3. Assumptions

- Missing Data for HBsAg are MANR
- The treatment effect is homogeneous across strata.

# 5.3.3.1.4. Missing Data Handling Rule

Participants who withdraw from the study prior to FU Week 24 will be considered non-responders. For the participants still in the study at FU Week 24 or for participants that have neither discontinued treatment early nor experienced any major protocol violations as listed in Table 9, but HBsAg values missing at FU Week 24, then the primary method to handle missing data will be the imputation to non-responder.

# 5.3.4. Hochberg Procedure

Consider testing the family of hypotheses  $H_{0i}$ , i = 1, ..., k.

Let  $p_i$ , i = 1, ..., k, denote the sample p-values of tests for  $H_{0i}$ , i = 1, ..., k, computed without multiplicity adjustment. Let [1], ..., [k] denote the random indices such that

 $p_{[1]} \leq \cdots \leq p_{[k]}.$ 

That is, [i] is the anti-rank of  $p_i$  among  $p_1, \ldots, p_k$ .

Hochberg's step-up method proceeds as follows.

Step 1. If  $p_{[k]} < a$ , reject  $H_{0[i]}$ , i = 1, ..., k, and stop; otherwise go to Step 2.

Step 2. If  $p_{[k-1]} < a/2$ , reject  $H_{0[i]}$ ,  $i = 1, \dots, k-1$ , and stop; otherwise go to Step 3.

. . .

Step k. If  $p_{[1]} < a/k$ , reject  $H_{0[i]}$ , i = 1, and stop.

# 5.4. Secondary Efficacy Endpoints

See Section 1.1 for a list of the secondary endpoints. All secondary endpoints will be analyzed using observed case data. Additional analyses with specific imputation methods for missing data are added for selected endpoints.

# 5.4.1. Definitions

# 5.4.1.1. Binary Endpoints

# 5.4.1.1.1. HBsAg Cut-offs

The cut-offs for HBsAg level are as follows (yes vs no):

- <1000 IU/mL
- <100 IU/mL
- <10 IU/mL
- <1 IU/mL
- <LLOQ (0.05 IU/mL)

The cut-offs for HBsAg change from baseline and Nivo RT are as follows (yes vs no):

- decrease by  $\geq 0.5 \log_{10} IU/mL$
- decrease by  $\geq 1 \log_{10} IU/mL$
- decrease by  $\geq 2 \log_{10} IU/mL$
- decrease by  $\geq 3 \log_{10} IU/mL$
- decrease by  $\geq 4 \log_{10} IU/mL$

The cut-offs for HBsAg change from FUW4 RT are as follows (yes vs no):

- increase by  $\leq 0.2 \log_{10} IU/mL$
- increase by  $\leq 0.5 \log_{10} IU/mL$
- increase by  $\leq 1 \log_{10} IU/mL$
- decrease by  $> 0.2 \log_{10} IU/mL$
- within +/- 0.2 log10 IU/mL

# 5.4.1.1.2. HBsAg Seroclearance

Seroclearance of HBsAg is defined as a (quantitative) HBsAg level <LLOQ (see Table 4). HBsAg seroclearance can be observed prior to the time point assessed but must be observed at the given week of interest.

HBsAg seroclearance will be evaluated over all time points when assessed, with emphasis at Week 24, FU Week 12, FU Week 32 and FU Week 48.

For the analyses of seroclearance at the time points mentioned above, participants with HBsAg seroclearance at the respective time points will be considered as having achieved this endpoint.

# 5.4.1.1.3. HBsAg Seroconversion

Seroconversion of HBsAg is defined as having achieved HBsAg seroclearance and appearance of anti-HBs antibodies.

The seroconversion will only be assessed at the time points when the anti-HBs antibodies assessment is available.

Appearance of anti-HBs antibodies is defined as a baseline anti-HBs antibodies (quantitative) <LLOQ and a post-baseline assessment  $\geq$ LLOQ. An additional seroconversion will be applied using the threshold of 10 mIU/mL, i.e. appearance of anti-HBs antibodies is defined as a baseline anti-HBs antibodies (quantitative) <10 mIU/mL and a post-baseline assessment  $\geq$ 10 mIU/mL.

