**The term “study intervention” throughout the protocol, refers to JNJ-3989 and nivolumab.**

**OBJECTIVES AND ENDPOINTS**

Below is the list of objectives and endpoints that will be evaluated in this study, delineating the details in alignment with the general objectives listed in the Master Protocol PLATFORMPAHPB2001. The details specific for this ISA are highlighted (colored fill).

| Objectives   | Endpoints   |
|--|---|
| Primary   |   |
| To evaluate efficacy of the study intervention, based on HBsAg levels at Follow-up Week 24 (FU Week 24). | 
 
Proportion of participants who achieve HBsAg seroclearance at FU Week 24.
 
   |
| Secondary   |   |
| To characterize the safety and tolerability of the study intervention.                                   | 
 
Proportion of participants who experienced adverse events (AEs) of interest.
 
Safety profile of JNJ-3989 with nivolumab throughout the study (safety parameters include but are not limited to the frequency and severity of AEs and immune-related AEs, vital signs measurements, physical examinations, clinical laboratory values, and 12-lead electrocardiograms [ECGs]).
 
 |

| Objectives  | Endpoints  |
|---|--|
| To evaluate efficacy in terms of changes in HBsAg levels from baseline over time during the study intervention and follow-up periods.                             | 
 
Change from baseline in HBsAg levels during the study intervention and follow-up periods.
 
Proportion of participants with HBsAg levels below/above different cut-offs over time.
 
  |
| To evaluate efficacy in terms of HBsAg seroclearance/seroconversion during the study intervention and follow-up periods (as defined in the Definitions of Terms). | 
 
Proportion of participants with HBsAg seroclearance/seroconversion during the study intervention and follow-up periods.
 
Time to achieve HBsAg seroclearance/seroconversion.
 
   |

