### 3. OBJECTIVES AND ENDPOINTS

Below is the list of objectives and endpoints that will be evaluated in this study, delineating the details in alignment with the general objectives listed in the Master Protocol PLATFORMPAHPB2001. The details specific for this ISA are highlighted (colored fill).

| Objectives   | Endpoints  |
|--|--|
| Primary   |  |
| To evaluate efficacy of the study intervention, based on HBsAg levels at FU Week 24.   | 
 
• Proportion of participants who achieve HBsAg seroclearance at FU Week 24.
 
  |
| Secondary   |  |
| To characterize the safety and tolerability of the study intervention.   | 
 
• Proportion of participants who experienced AEs of interest.
 
• Safety profile of JNJ-3989 with nivolumab throughout the study (safety parameters include but are not limited to the frequency and severity of AEs and immune-related AEs, vital signs measurements, physical examinations, clinical laboratory values, and 12-lead electrocardiograms [ECGs]).
 
 |
| To evaluate efficacy in terms of changes in HBsAg levels from baseline over time during the study intervention and follow-up periods.  | 
 
• Change from baseline in HBsAg levels during the study intervention and follow-up periods.
 
• Proportion of participants with HBsAg levels below/above different cut-offs over time.
 
  |
| To evaluate efficacy in terms of HBsAg seroclearance/seroconversion during the study intervention and follow-up periods (as defined in the Definitions of Terms ). | 
 
• Proportion of participants with HBsAg seroclearance/seroconversion during the study intervention and follow-up periods.
 
• Time to achieve HBsAg seroclearance/seroconversion.
 
   |

| Objectives  | Endpoints   |
|---|---|
| To evaluate the efficacy as measured by blood markers (such as HBV DNA and HBeAg) during the study intervention and follow-up period.                   | 
 
Change from baseline in HBV DNA levels during the study intervention and follow-up periods.
 
Proportion of participants with HBV DNA and HBeAg levels below/above different cut-offs over time.
 
 |

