## Definitions of Terms

|                               |  |
|-------------------------------|--|
| ALT/AST nadir                 | Lowest ALT/AST value during study participation  |
| End of study intervention     | Time of the last administration of study intervention  |
| Functional cure               | HBsAg seroclearance at 24-weeks after EOSI   |
| HBsAg or HBeAg seroclearance  | HBsAg or HBeAg negativity, respectively, based on the assay used   |
| HBsAg or HBeAg seroconversion | HBsAg or HBeAg negativity and anti-HBs or anti-HBe antibody positivity, respectively   |
| IC 50              | half maximal inhibitory concentration  |
| Study intervention            | JNJ-73763989 (JNJ-3989) and nivolumab  |
| Background treatment          | NA (either ETV, tenofovir disoproxil, or TAF)  |
| Virologic breakthrough        | Confirmed on-treatment HBV DNA increase by >1 log 10 IU/mL from nadir or confirmed on-treatment HBV DNA level >200 IU/mL in participants who had HBV DNA level <LLOQ of the HBV DNA assay |

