## 5.5.2.2.2. Anti-HBs Antibodies

For all participants with positive anti-HBs antibodies at baseline who will reach HBsAg seroclearance (as defined in Section 5.4.1.1.2), descriptive statistics will be calculated for the change of anti-HBs antibodies level from baseline at the timepoint and subsequent timepoints when achieving the HBsAg seroclearance. In an additional summary, the change of anti-HBs antibodies level from baseline at the specific timepoint and subsequent timepoints will be summarized descriptively for the subset of the participants achieving HBsAg seroclearance at any time before or at that given timepoint.

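### SAP 5.4.1.1.3 adds an unrecorded baseline condition to HBsAg seroconversion, making it narrower than the protocol's definition and leaving its two thresholds non-nested

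*SAP*

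**What the plan says.** Protocol Appendix 1 (Definitions of Terms) defines HBsAg or HBeAg seroconversion as "HBsAg or HBeAg negativity and anti-HBs or anti-HBe antibody positivity, respectively". It sets no condition on the baseline antibody level and gives no numeric cut-off for positivity. The endpoint is a named secondary one in Protocol Section 3: "Proportion of participants with HBsAg seroclearance/seroconversion during the study intervention and follow-up periods". The matching objective points to the same definition by name: "HBsAg seroclearance/seroconversion during the study intervention and follow-up periods (as defined in the Definitions of Terms").

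SAP 5.4.1.1.3 words it differently: "Seroconversion of HBsAg is defined as having achieved HBsAg seroclearance and appearance of anti-HBs antibodies". It then gives two versions of appearance.

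- Main: "Appearance of anti-HBs antibodies is defined as a baseline anti-HBs antibodies (quantitative) <LLOQ and a post-baseline assessment" at or above LLOQ.
- Additional: "An additional seroconversion will be applied using the threshold of 10 mIU/mL", that is, "baseline anti-HBs antibodies (quantitative) <10 mIU/mL and a post-baseline assessment" of at least 10 mIU/mL.

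SAP Table 4 gives the anti-HBs LLOQ as 5 mIU/mL. SAP 5.4.2.1 reports the count and proportion of participants meeting each binary endpoint on observed-case data, with a 90% CI for seroconversion. SAP Appendix 2 says only, in general terms, that changes to protocol-planned analyses are documented in the SAP. Neither it nor the version history mentions a baseline condition for seroconversion.

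**The concern.** The protocol describes a status at a visit. The SAP describes a change from baseline. The two give the same answer for anyone below the threshold at baseline and can differ for anyone else.

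The plan itself allows for the second group. No eligibility criterion in Protocol 5.1 or 5.2 concerns anti-HBs. SAP Table 8 tabulates baseline anti-HBs status and a below-10 versus 10-or-more category. SAP 5.5.2.2.2 plans a summary "For all participants with positive anti-HBs antibodies at baseline who will reach HBsAg seroclearance". That summary covers change in antibody level only and gives these participants no seroconversion status.

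Two things are at stake. A participant who meets the protocol's secondary endpoint can be reported as not meeting it, with nothing in the SAP to warn the reader. And the count at the stricter 10 mIU/mL threshold can exceed the count at the looser one, which a reader would take for an error.

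**Working it through.** The plan states no figure for this endpoint, so there is none to reproduce. The check applies each rule to possible antibody values.

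**Inputs.** b is baseline and p is post-baseline anti-HBs in mIU/mL. HBsAg seroclearance is taken as met at the visit. LLOQ = 5 (SAP Table 4); values below LLOQ are set to 2.5 (same table).

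**Rules.**

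- SAP main: b < 5 and p ≥ 5.
- SAP additional: b < 10 and p ≥ 10.
- Protocol: p positive. With no cut-off given, it is applied at p ≥ 5 and at p ≥ 10.

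| b | p | SAP main (5) | SAP additional (10) | Protocol at 5 | Protocol at 10 |
|---|---|---|---|---|---|
| 2.5 | 7 | yes | no | yes | no |
| 2.5 | 15 | yes | yes | yes | yes |
| 7 | 7 | no | no | yes | no |
| 7 | 15 | no | yes | yes | yes |
| 10 | 15 | no | no | yes | yes |
| 50 | 200 | no | no | yes | yes |

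**Results.**

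1. Under the main rule every case with b ≥ 5 is a no, whatever p is. Under the additional rule this holds only for b ≥ 10. A baseline from 5 to just under 10 can succeed there.
2. At the same threshold, each SAP rule is the protocol rule plus a further condition. The SAP count can therefore equal the protocol count or fall below it, but never exceed it.
3. The SAP rules are not nested. The 7-to-15 case meets only the 10 mIU/mL rule, and the 2.5-to-7 case meets only the 5 mIU/mL rule. Without the baseline condition the rules are p ≥ 5 and p ≥ 10, and everyone in the second is in the first.

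**Size.** The documents give no baseline anti-HBs distribution, so the number affected cannot be computed. What can be shown is the weight of one person: 1/18 = 5.6 percentage points in Arm 1 and 1/19 = 5.3 in Arm 2. Suppose, purely as an assumption, that 2 of 19 in Arm 2 meet the protocol definition and one of them had b ≥ 5.

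- Protocol definition: 2/19 = 10.5% (Clopper-Pearson 90% CI 1.9 to 29.6).
- SAP main rule, all 19 in the denominator: 1/19 = 5.3% (0.3 to 22.6).

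**Denominator.** The direction of the effect on the rate depends on a choice the SAP does not state. Suppose instead that 3 of the 19 are baseline-positive, none of them clears HBsAg, and 2 of the other 16 seroconvert. The protocol rate is 2/19 = 10.5%. The SAP rate is also 2/19 if the 3 stay in, but 2/16 = 12.5% if they are left out.

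**The case against.** The best defence is that conversion implies change. A person who already has anti-HBs and then loses HBsAg has not newly acquired antibody, and the protocol leaves technical detail to the SAP. On this view the SAP has refined a loose definition. That stands as a defence of the concept. It does not explain why a rule narrower than the definition the objective cites is absent from the list of changes.

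Three stronger readings are tempting, and the documents do not support them.

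- A reader might infer that anyone with anti-HBs of 5 mIU/mL or more at baseline can never seroconvert under the SAP. That is true of the main rule only; the additional rule admits baselines from 5 to just under 10.
- A reader might infer that baseline-positive participants stay in the denominator, so the reported rate is biased downward. That is the natural reading of SAP 5.4.2.1, but the SAP does not say so.
- A reader might call the two documents contradictory. The SAP rule is a restriction of the protocol rule, and the protocol sets no numeric cut-off with which it could conflict.

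It is also fair to say that baseline-positive clearers are not lost from the report: SAP 5.5.2.2.2 describes their antibody levels. What they lack is a seroconversion status. Each SAP rule can also be interpreted alone, as a count of people crossing a stated level from below. The difficulty arises when the two are read side by side as a looser and a stricter version of one endpoint.

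**Conclusion.** The point holds as a definitional gap. SAP 5.4.1.1.3 narrows a secondary endpoint that the protocol defines, does not record having done so, moves the baseline cut-off with the threshold so that the two versions are not nested, and leaves the denominator unstated. All of this follows from the wording and needs no assumption about the data.

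The practical size is unknown and could be zero. It depends on how many participants have both measurable anti-HBs at baseline and HBsAg seroclearance later. The second group may be small: SAP Amendment 2 dropped the subgroup analyses because few events had been seen. The 2-of-19 example shows only how far one reclassified person moves the estimate in arms of 18 and 19; it is no evidence that anyone was misclassified. The primary endpoint, its test and the sample size are unaffected, because seroclearance does not involve anti-HBs.

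**What to change.** 1. In SAP 5.4.1.1.3, score seroconversion by the protocol definition: HBsAg below LLOQ and anti-HBs at or above the threshold at the same visit, for all participants with data, at both 5 and 10 mIU/mL. The two counts are then nested.
2. Keep new appearance of anti-HBs with seroclearance as a separate, labelled line at each threshold. Its denominator is the participants below that same threshold at baseline.
3. Record the difference between the two concepts in SAP Appendix 2.

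The cost is SAP wording, one derived variable and an extra table line; all the data are already collected. The downside is that a participant with pre-existing anti-HBs counts as a seroconverter on clearing HBsAg. The separate line makes such cases visible. Since SAP Amendment 2 was written after the primary analysis, the change should be dated and both lines always shown, so that no one can suspect the definition was picked for its result.

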# 5.4.1.1.4. HBeAg Cut-offs

The cut-offs for HBeAg level are as follows (yes vs no):

- < LLOQ
- <1 IU/mL
- <10 IU/mL

# 5.4.1.1.5. HBV DNA Cut-offs

The cut-offs for HBV DNA are as follows (yes vs no):

- < LLOQ for target detected or not detected
  - < LLOQ for target not detected
  - < LLOQ for target detected
- <60 IU/mL
- <200 IU/mL
- <2000 IU/mL
- <20000 IU/mL

# 5.4.1.1.6. Suppressed HBV DNA

HBV DNA < LLOQ (HBV DNA detectable or HBV DNA TND) and HBV DNA < 60 IU/mL will be evaluated over all time points when assessed, with emphasis at Week 24, FU Week 12, FU Week 24, FU Week 32 and FU Week 48.

# 5.4.1.1.7. ALT Normalization

ALT elevation at baseline is defined as ALT≥ULN. A participant with ALT elevation at baseline achieves ALT normalization if his/her ALT value post-baseline is <ULN at any given time point.

Participants who achieve ALT normalization on treatment will be evaluated over time.

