## 5.1. Inclusion Criteria

Each potential participant must satisfy all of the following criteria to be enrolled in the study:

- A01 (adapted from M01) Adult male or female participants  $\geq 18$  (or the legal age of consent in the jurisdiction in which the study is taking place) to  $< 56$  years of age.
- M02 Participants must be medically stable based on physical examination, medical history, vital signs, and 12-lead ECG performed at screening. If there are abnormalities, they must be consistent with the underlying illness in the study population. This determination must be recorded in the participant's source documents and initialed by the investigator.
- A03 (adapted from M03a) Participants must have chronic HBV infection. HBV infection must be documented by serum HBsAg positivity at screening. In addition, chronicity must be documented by any of the following, at least 6 months prior to screening: serum HBsAg positivity, HBeAg positivity or HBV DNA positivity, ALT elevation  $> \text{ULN}$  without another cause than HBV infection, documented transmission event, liver biopsy with changes consistent with chronic HBV, or absence of marker for acute HBV infection at screening such as positive immunoglobulin M (IgM) anti-HBc antibodies.
- Participants should:
- Be HBeAg negative at screening, AND
  - Be on stable HBV treatment, defined as currently receiving NA treatment (ie, entecavir, tenofovir disoproxil, or tenofovir alafenamide) for at least 12 months prior to screening, and having been on the same NA treatment regimen (at the same dose) as used in this study (see Table 4) for at least 3 months at the time of screening, AND
  - Have serum HBV DNA  $< 60$  IU/mL on 2 sequential measurements at least 6 months apart (one of which is at screening), AND
  - Have documented ALT values  $< 2.0 \times \text{ULN}$  on 2 sequential measurements at least 6 months apart (one of which is at screening).
- A04 (adapted from M04) Participants must have a body mass index (BMI; weight in kg divided by the square of height in meters) between 18.0 and 30.0  $\text{kg/m}^2$ , extremes included.
- A05 (adapted from M05) Participants must sign a Master ICF (specific for the Master Protocol PLATFORMPAHPB2001) and must sign an ICF specific for this intervention cohort, indicating that he or she understands the purpose of, and procedures required for, the study and is willing to participate in the study.

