# 5.1.4. Baseline

In general, the baseline assessment is defined as the last observed non-missing measurement before the date and time of the first administration of any of study agents.

In case the first administration measurement time is missing, the first observed measurement on SI Day 1 will be used as the baseline measurement. If no observed measurement on Day 1, the last observed measurement before Day 1 will be used as the baseline assessment.

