## 5.4.1.1.9. Flares

The criteria based on blood markers/lab tests for each of the flare types are defined below.

**On-treatment Biochemical flare** is defined as follows:

The start date of a confirmed on-treatment biochemical flare is defined as the first date of two consecutive visits with ALT and/or AST $\ge$ 3x ULN and  $\ge$ 3x nadir (i.e. lowest value observed up to the start of the flare) while the participant receives any of the study interventions. The end date of the same on-treatment biochemical flare is defined as the first date when there is a 50% reduction from the peak ALT and/or AST level & <3x ULN, regardless of stopping the study interventions.

- 1 (Yes) = confirmed\*\* ALT and/or AST ≥3x ULN and ≥3x nadir (i.e. lowest value observed up to the start of the flare)
- 0 (No) = otherwise

\*\* Confirmed means that the criterion should be fulfilled at 2 or more consecutive time points or at the last observed time point.

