Change from baseline based on  $log_{10}$  transform for quantitative HBsAg, HBeAg and HBV DNA will be analyzed using mixed effects model for repeated measures [MMRM]) including intervention arm, analysis time point (week), and the randomization stratification factor (ie, absolute HBsAg value at screening [<100 IU/mL, 100 to <1,000 IU/mL versus  $\geq$ 1,000 IU/mL]) as fixed effects. In addition, the above model will be augmented with an intervention arm-by-analysis week interaction term (i.e. treatment-by-time interaction term) to evaluate the change of treatment effect over time. The covariance structure will include a random intercept at the level of the participant to capture between-participant variability, while within-participant variability will be captured with an unstructured (type=UN) covariance matrix. In case of convergence problems, simpler variance-covariance structures such as Toeplitz or AR (1) will be considered. The selection of any of these structures will be determined after exploration of the observed correlation structure. The LS mean of change from baseline, standard error (SE), 90% confidence interval (CI) and p-values will be provided.

Descriptive statistics on actual values (original unit and  $log_{10}$  transformed values) in HBsAg, HBeAg and HBV DNA and changes from baseline ( $log_{10}$  transformed values) at end of treatment

in HBsAg, HBeAg and will be summarized by study intervention arm by outcome response (i.e. by HBsAg seroclearance at FU Week 24 and FU Week 48).

Waterfall plots for actual values, changes from baseline of HBsAg will also be presented.

Descriptive statistics of the absolute values, changes from baseline over time in ALT will be summarized by intervention arm and analysis phase for those participants who had ALT elevation at baseline. An additional summary of descriptive statistics of the ALT absolute values and changes from baseline over time will be summarized by intervention arm and analysis phase for those participants who had ALT values within the normal range at baseline.

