Baseline ALT categorization: ≤ 1.0xULN, > 1.0xULN to <2xULN, ≥ 2xULN	

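### SAP 5.4.1.1.7 counts ALT exactly at ULN as elevated although the rest of the plan treats it as normal, and its single-value normalization rate needs a regression-to-the-mean caveat

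*SAP*

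**What the plan says.** - **Who is elevated.** SAP 5.4.1.1.7: "ALT elevation at baseline is defined as ALT≥ULN".
- **Who responds.** Same section: that participant "achieves ALT normalization if his/her ALT value post-baseline is <ULN at any given time point". No minimum change and no second value is required.
- **Baseline.** SAP 5.1.4: "the baseline assessment is defined as the last observed non-missing measurement before the date and time" of first dosing, so one value decides who enters the denominator.
- **Entry.** Protocol 5.1, criterion A03, requires ALT below 2.0x ULN "on 2 sequential measurements at least 6 months apart (one of which is at screening").
- **Baseline categories.** SAP Table 8: "Baseline ALT categorization: ≤ 1.0xULN, > 1.0xULN to <2xULN", then a category for 2x ULN and above.
- **Toxicity grading.** In the modified DAIDS table (protocol Appendix 8), Grade 1 ALT starts above 1.0x ULN. In SAP 5.6.3.1 a high post-baseline value is one above the upper limit.
- **Subgroup summaries.** SAP 5.4.2.2.1 summarizes ALT for those with ALT elevation at baseline and, separately, for "participants who had ALT values within the normal range at baseline".
- **Analysis.** SAP 5.4.2.1 reports ALT normalization as a count and percentage with a 90% CI, on observed cases.

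**The concern.** There are two separate issues.

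First, the plan draws the normal/elevated line in two places. A participant whose ALT equals ULN at baseline and at every later visit has not changed. SAP 5.4.1.1.7 nevertheless records an elevated participant who never normalized, while Table 8 and the DAIDS grading record a participant who was normal throughout. The two ALT subgroups in 5.4.2.2.1 are meant to be distinct, but as worded they can overlap.

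Second, selecting people on one value at or above a line, then scoring one later value below that line, produces some apparent normalization without any treatment effect. There is no nivolumab-free arm to show how much. A single-arm percentage with its CI could then be taken for biochemical benefit.

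**Working it through.** **1. The boundary, side by side**

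| Place | How ALT = ULN is classed |
|---|---|
| SAP 5.4.1.1.7, baseline | Elevated |
| SAP 5.4.1.1.7, post-baseline | Not normalized |
| SAP Table 8 | Lowest category (up to and including 1.0x ULN) |
| Protocol Appendix 8, modified DAIDS | Below Grade 1 |
| SAP 5.6.3.1 | Not high |
| SAP 5.4.2.2.1, elevated subgroup | Included, through 5.4.1.1.7 |
| SAP 5.4.2.2.1, normal-range subgroup | Included, if the range contains its upper limit |

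This comparison needs no assumption except in the last row, because 5.4.2.2.1 does not define the normal range.

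**2. How many people the boundary touches**

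The documents do not say. Assuming integer ALT results and a ULN of 34–45 U/L, about 7–9% of those classed as elevated would sit exactly at ULN. With 2–11 elevated participants among 37 (step 3), that is 0.07 × 2 = 0.14 to 0.09 × 11 = 0.99, so about one person at most.

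**3. Regression to the mean**

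The plan states no expected rate for ALT normalization, so there is no figure to reproduce.

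- From the documents: two entry values below 2.0x ULN; one baseline value at or above ULN; response is one value below ULN; nine post-baseline chemistry visits to Week 24; 37 participants.
- Assumed: median true ALT 0.6, 0.7 or 0.8x ULN; between-person SD of log ALT (s_b) 0.3, 0.4 or 0.5; within-person CV 10, 15, 20, 25 or 30%. This gives 3 × 3 × 5 = 45 combinations.
- Model: T ~ N(ln median, s_b²) is the true log(ALT/ULN). Each measured value is T + s_w·Z, with Z standard normal and s_w = √ln(1 + CV²). Keep those with both entry values below ln 2 and baseline ≥ 0. There is no treatment effect. Each combination used 3,000,000 simulated participants.

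The middle case is median 0.7, SD 0.4, CV 20%.

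| Quantity with no effect | Lowest | Middle case | Highest |
|---|---|---|---|
| Below ULN at one visit | 14% | 37% | 66% |
| Below ULN at two consecutive visits (a fixed pair) | 7% | 22% | 49% |
| Same, with elevation at both screening and baseline | 3% | 10% | 31% |
| Below ULN at least once in nine visits | 36% | 78% | 98% |
| Elevated participants out of 37 | 2 | 7 | 11 |

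In a continuous model equality has probability zero, so these rates are the same under either boundary. Lowering the median to 0.5x ULN raises the one-visit maximum to 75%, but then only about 0.5–4 of 37 would be elevated.

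**4. Closed-form check**

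For a fixed true ALT of t × ULN, P(value below ULN) = Φ(−ln t / s_w). At CV 20%, s_w = √ln 1.04 = 0.198:

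- t = 1.0: Φ(0) = 50%
- t = 1.1: Φ(−0.0953/0.198) = 31%
- t = 1.2: Φ(−0.1823/0.198) = 18%
- t = 1.3: Φ(−0.2624/0.198) = 9%
- t = 1.5: Φ(−0.4055/0.198) = 2%

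Chance crossing is substantial near ULN and fades quickly above it.

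**5. Per visit or ever**

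The middle case moves from 37% to 78% depending on which reading of the definition is used. The section adds that normalization is evaluated over time, and SAP 5.4.2.1 analyses binary endpoints at every time point, so per visit is the natural reading. The definition does not say so outright.

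**The case against.** The case for leaving the section alone is a fair one.

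- **Single-visit scoring is the plan's pattern.** Seroclearance, suppressed HBV DNA and the antigen cut-offs are all scored on one visit's value. Confirmation is required for flares and virologic breakthrough, which are linked to repeat testing and stopping rules. Even there, the flare rule accepts one final value: "Confirmed means that the criterion should be fulfilled at 2 or more consecutive time points or at the last observed time point". This stands, so the absence of confirmation for ALT is a choice and not an inconsistency.
- **Context is already planned.** ALT values and changes by baseline subgroup, shift tables and spaghetti plots will show the size and persistence of changes. This also stands.
- **Both arms are affected alike.** Regression to the mean does not favour either randomized arm. It misleads only when one arm's percentage is read alone.
- **A redefinition now would be post hoc.** SAP Amendment 2 (10 June 2024) was written in light of the primary analysis results. This stands against replacing the planned definition, but not against a labelled addition.
- **The boundary affects almost nobody.** Agreed, but it is still a classification rule that contradicts the rest of the plan.

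A reader might infer that every elevated participant sits just above ULN. Criterion A03 does not support that: it caps the screening value and an earlier one but not Day 1 ALT, and Table 8 has a category for 2x ULN and above.

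**Conclusion.** The boundary rule in SAP 5.4.1.1.7 is wrong as written, because it contradicts Table 8, the DAIDS grading and 5.6.3.1, and it lets one participant fall into both ALT subgroups. The practical size is probably one participant at most.

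The regression-to-the-mean point holds as a caution. The one-visit rate with no effect is about 14–66%, resting wholly on an assumed median, between-person SD and within-person CV. None of these is in the documents.

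Two stronger readings are tempting and not supported. One is to quote a narrower rate as fact: 80% of the 45 combinations fall within 18–50%, but nothing in the documents favours those combinations. The other is that most observed normalization would be noise. That cannot be said without the observed rate, and the no-effect rate may be as low as 14%.

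Overall impact is minor. ALT normalization is descriptive, is absent from the objectives tables in both documents, and plays no part in the primary test.

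**What to change.** 1. In SAP 5.4.1.1.7 define elevation as ALT above ULN and normalization as ALT at or below ULN. Use the same line for the two ALT subgroups in 5.4.2.2.1, so that both sections agree with Table 8.
2. State that normalization is scored at each visit, not as ever achieved.
3. Keep the planned per-visit proportion. Report beside it, labelled as added after the primary analysis, a version requiring ALT above ULN at both screening and baseline and at or below ULN at two consecutive scheduled visits. Under the assumptions above its no-effect rate for a given pair of visits is about 3–31%. It reduces chance normalization without removing it, since the same line still selects and scores.
4. Add a sentence that single-arm proportions are not to be read as treatment effect.

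The cost is SAP wording and one extra derivation on values already collected. The downside of the confirmed version is a smaller denominator, when the planned one is already only about 2–11 of 37 under the same assumptions.
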